### 8.6 Assessment of Causality

Causal relationship assessment to drug treatments is required for purposes of reporting AEs. To promote consistency, the following guidelines should be taken into

considerations along with good clinical and scientific judgment when determining the relationship of drug treatments to an AE:

Definitely Related: A clinical event, including laboratory test abnormality, occurring in

a plausible time relationship to the medication administration, and which cannot be explained by concurrent disease or other drugs or chemicals. The response to withdrawal of the drug should be

clinically plausible.

Possibly Related: A clinical event, including laboratory test abnormality, with a

reasonable time sequence to the medication administration, but which could also be explained by concurrent disease or other drugs or chemicals. Information on the drug withdrawal may be lacking

or unclear.

Unlikely Related: A clinical event, including laboratory test abnormality, with little or

no temporal relationship to medication administration, and which other drugs, chemicals or underlying disease provide plausible

explanations.

Not Related: A clinical event, including laboratory test abnormality that has no

temporal relationship to the medication or has more likely

alternative etiology.

# 8.7 Assessment of Severity

Adverse events are to be graded according to the categories detailed below.

Mild: Mild events are those which are easily tolerated with no disruption

of normal daily activity.

Moderate: Moderate events are those which cause sufficient discomfort to

interfere with daily activity.

Severe: Severe events are those which incapacitate and prevent usual

activity.

Changes in severity should be documented in the medical record to allow assessment of the duration of the event at each level of severity. Adverse events characterized as intermittent require documentation of the start and stop of each incidence. When changes

in the severity of an AE occur more frequently than once a day, the maximum severity for the experience that day should be noted. If the severity category changes over a number of days, then those changes should be recorded separately (with distinct onset dates).

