Safety Assessments:	26. Safety evaluations will include assessment of adverse events (AEs), electrocardiograms (ECGs), cardiac monitoring (telemetry), arterial oxygen saturation (SaO 2 ) using pulse oximetry, vital signs (blood pressure, pulse rate, oral body temperature, and respiration rate), clinical laboratory safety tests (hematology, serum chemistry, liver function tests, thyroid function parameters, serology, coagulation parameters, urinalysis, cytokines, C-reactive protein, complement factors), and physical examinations.
Other Assessments:	

27. Exploratory effects of ALN-TTR02 will be evaluated by:

28. Serial measurement of circulating mutant and wild type TTR levels

	
 
29. Serial measurement of circulating vitamin A and retinol binding protein (RBP) levels
 
Blood collections to explore the expression of hepatocyte derived proteins to further characterize the biological effects of siRNA LNPs.
 

Amendment 2.1 Confidential Page 15 of 116

Dose-Limiting	Dose-limiting toxicities will include any of the following:	
Toxicities and Stopping Criteria:	1. Any life-threatening toxicity.	
Stopping Criteria.	2. ALT and AST ≥5 × ULN or total bilirubin >2.0 mg/dL.	
	3. An infusion reaction that requires hospitalization, despite premedication.	
	4. Any other toxicity which in the opinion of the SRC precludes further dosing.	
	Stopping Rules:	
	For any DLT, accrual to that dose level will stop, all dosing will be discontinued, and dose escalation will end, pending further evaluation of all available safety data by the SRC.	
Statistical Methods:	Statistical analyses will be primarily descriptive in nature.  Adverse event summaries will include tabulations of all treatment-emergent AEs, treatment-related AEs, serious adverse events (SAEs), discontinuations due to AEs, and AEs of various grading severity. By-patient listings will be provided for deaths, SAEs, and AEs leading to discontinuation of treatment.	
	Descriptive statistics will be provided for clinical laboratory data, vital signs data, and ECG interval data, presented as both actual values and changes from baseline relative to each onstudy evaluation. Laboratory shift tables from baseline to worst values will be presented.	

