#### 8.3 **Eliciting Adverse Event Information**

The patient should be asked about medically relevant changes in his/her health since the last visit. The patient should also be asked if he/she has been hospitalized, had any accidents, used any new medications, or changed concomitant medication routines (both prescription and OTC).

In addition to patient observations, AEs will be documented from any laboratory findings, physical examination findings, ECG changes or other documents.

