Tabulations by SOC and preferred term will be produced for all TEAEs, for all related TEAEs, all TEAEs of severe intensity, all treatment-emergent IRRs, and for all serious TEAEs. In these tabulations, each subject will contribute only once (i.e., the most related occurrence or the most intense occurrence) to each of the incidence rates in the descriptive analysis, regardless of the number of episodes of a given event (preferred term). The most commonly occurring TEAEs, defined as those events experienced by at least 10% of all subjects, will be tabulated by preferred term in decreasing order in frequency.

Separate tables will present AE incidence rates by maximum relationship to study drug and by maximum severity. Subjects who report multiple occurrences of the same AE (preferred term) will be classified according to the most related or most severe occurrence, respectively.

No formal hypothesis-testing of AE incidence rates will be performed.

All reported AEs will be provided in data listings, including AEs that are not treatment-emergent.

By-subject listings also will be provided for the following: subject deaths, SAEs, AEs leading to drug discontinuation, and DLTs.

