4.5.3. Laboratory Data

Clinical laboratory values will be expressed in SI units.

Descriptive statistics will be provided for the actual values and changes from baseline to each on-study evaluation for each clinical laboratory parameter, including hematology, clinical chemistry, LFTs, thyroid function tests, and coagulation studies. Percent change from baseline will also be summarized.

Descriptive statistics will be provided for CRP and cytokines at pre-dose and 2, 6, and 24 hours post-dose. Change from pre-dose will also be summarized. Fold change, as defined below, will be summarized for CRP. Complement factor (Bb) will be summarized at pre-dose, and 30 minutes, 2 hours and 24 hours post-dose. Change and fold change from pre-dose will also be summarized. Separate summaries will be presented for Dose 1 and Dose 2.

Fold change from pre-dose is defined as the ratio of the post-dose value to the pre-dose value. Maximum fold change is defined as the ratio of the maximum post-dose value to the pre-dose value. Maximum fold change from pre-dose for cytokines, complement factor (Bb), and CRP will be represented graphically in the form of a semi- \log_{10} plot. Maximum fold change will be plotted for each subject, grouped by dose level. Data recorded as below the limit of detection will be set equal the lower limit of detection for the calculation of fold change. Separate plots will be presented for Dose 1 and Dose 2.

For each continuous laboratory parameter, results will be categorized as low, normal, or high based on the laboratory normal ranges. Shift tables will be employed to summarize the pre-dose category versus the post-dose category, where the post-dose category will be based on the maximum observed value (in absolute value) subsequent to each dose. For dose 1, the maximum value shall be selected from assessments performed through the Day 28 pre-dose

value (Day 21 for the 3-week regimen). All out-of-range and clinically significant laboratory results will be identified in subject data listings.

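### Protocol 8.7 grades every adverse event by its effect on daily life, so a symptom-free liver-enzyme rise that is a dose-limiting toxicity is recorded as Mild and drops out of the severe-event tables

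*Protocol*

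**What the plan says.** Protocol 8.1 includes abnormal laboratory findings in the AE definition. Protocol 8.3 adds that "AEs will be documented from any laboratory findings, physical examination findings, ECG changes or other documents". Protocol 8.6 names laboratory abnormalities in each of its four causality categories.

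Protocol 8.7 then sets a single scale: "Adverse events are to be graded according to the categories detailed below". The three levels are:

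- Mild: "Mild events are those which are easily tolerated with no disruption" of ordinary activity.
- Moderate: "Moderate events are those which cause sufficient discomfort to" interfere with the patient's day.
- Severe: "Severe events are those which incapacitate and prevent usual" activity.

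The liver DLT in the Protocol synopsis is a laboratory threshold with no symptom condition: "ALT and AST ≥5 × ULN or total bilirubin >2.0 mg/dL". Protocol 5.7.3 repeats it with a slightly different bilirubin sign (at or above 2.0 mg/dL, against above 2.0 mg/dL in the synopsis). Those two places must be reconciled, but the difference does not affect this point. Under Protocol 5.7.4 any DLT stops accrual and dosing until the Safety Review Committee has looked at the data.

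SAP 4.5.2 counts patients with a severe treatment-emergent AE (TEAE), counts patients with a DLT separately, and states: "Separate tables will present AE incidence rates by maximum relationship to study drug and by maximum severity". For the laboratory shift tables, SAP 4.5.3 says that "results will be categorized as low, normal, or high based on the laboratory normal ranges".

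**The concern.** The primary objective is safety and tolerability, and the severity tables are among its main summaries. A scale built on what the patient feels has no term for the size of a finding. For an abnormality without symptoms it returns the lowest level whatever the value. The same event can then be the reason the trial paused and also a Mild AE in the clinical study report, beside a severe-event table that shows zero. The direction is systematic, because on the literal wording a silent finding can only be graded low. An investigator may depart from the wording for a large rise, but nothing in 8.7 provides for that. With up to 10 centres, such departures would not be uniform.

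**Working it through.** The plan states no figure to reproduce here. The check applies 8.7 literally and follows the result through the SAP outputs.

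**Step 1: the grade.** Take a patient without symptoms whose ALT and AST are both at the stated multiple of ULN. Activity is not disrupted and the patient is not incapacitated.

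| ALT and AST (× ULN) | Grade under 8.7 | Liver DLT criterion met |
|---|---|---|
| 2.6 | Mild | no |
| 5 | Mild | yes |
| 10 | Mild | yes |
| 20 | Mild | yes |

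**Step 2: where a DLT-level event appears.**

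| Output | Appearance |
|---|---|
| Severe-TEAE row of the overview (Table 14.3.1.1) | not counted |
| Severe TEAEs, and severe related TEAEs (14.3.1.4, 14.3.1.5) | absent |
| TEAEs by maximum severity (14.3.1.10) | under Mild |
| DLT count in the SAP 4.5.2 overview | counted |
| DLT listing (14.3.2.4) | listed |
| All TEAEs (14.3.1.2), and related TEAEs if judged related (14.3.1.3) | included |
| Liver-test summaries, individual plots, abnormal-value listing (SAP 4.5.3) | value shown |

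**Step 3: do the laboratory tables show the size?**

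- Shift tables have three categories. From a normal baseline, peaks of 1.1 × and 10 × ULN both read normal to high.
- Protocol 4.2 admits patients with AST and ALT up to 2.5 × ULN. A patient who starts above ULN and reaches 5 × ULN reads high to high, which is no shift.
- Percent change does not recover the multiple. From 2.5 to 5 × ULN it is (5 − 2.5)/2.5 = 100%. From 1 to 5 × ULN it is (5 − 1)/1 = 400%. From 1 to 2 × ULN it is again (2 − 1)/1 = 100%.
- Actual values are summarised in SI units, while the tests are run at each centre's local laboratory (Protocol 7.2.7). A group maximum is therefore not expressed against the ULN that applied to that patient.

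The values reach the report, but no tabulation expresses them in the unit in which the protocol defines enzyme eligibility and toxicity.

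**Step 4: illustrative size.** Assume one symptom-free patient with a DLT-level rise, and a magnitude scale that would call it severe. The severe row changes from 0/n to 1/n:

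- one cohort: 0/3 against 1/3 = 33.3%
- pooled dose group of 6: 0/6 against 1/6 = 16.7%
- pooled dose group of 9: 0/9 against 1/9 = 11.1%
- all patients: 0/27 against 1/27 = 3.7%, with 27 = 4 × 3 + 5 × 3 (SAP 3.1)

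**The case against.** A functional intensity scale used alongside separate reporting of DLTs, seriousness and laboratory values is a coherent design, and no decision in the trial depends on the severity tables. The committee works from the data themselves and from the DLT rule. The analysis is descriptive, without hypothesis tests. All of that stands, and it limits the weight of the point.

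A reader might infer more than the documents support in four ways:

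- *That the event is missing from the safety report.* It is not. It is absent from the severe rows only, and Step 2 shows where else it appears.
- *That the SAP classes laboratory values only as low, normal or high.* That is true of the shift tables alone. SAP 4.5.3 also gives actual values, changes, percent changes, individual liver-test plots, and listings with comments on clinical significance. With three patients in a cohort, a very high value would be visible there.
- *That other silent findings, such as a marked platelet fall, an arrhythmia seen only on telemetry, or a rise mainly in one transaminase, cannot be caught.* The fourth DLT criterion leaves room for the committee's judgement. The important-medical-event criterion in Protocol 8.2 can make such a finding serious. Eligibility is also rechecked before the second dose (Protocol 5.6).
- *That severe incidence is biased by 33 percentage points.* That figure is 1/n against 0/n for one assumed event under an assumed scale.

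Protocol Appendices 1 and 2 classify infusion reactions by the intervention needed. They do not cover laboratory or ECG findings and do not close the gap.

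**Conclusion.** The point holds in a limited form. Following Protocol 8.1, 8.3 and 8.7 exactly, a symptom-free ALT and AST rise at or above 5 × ULN is a Mild AE and a DLT at the same time. It does not enter the severe-TEAE row or Tables 14.3.1.4 and 14.3.1.5, and no tabulation gives its size in multiples of ULN. The defect lies in labelling and tabulation: the event is not concealed, and the stopping rule works independently of 8.7. The conclusion rests on the literal wording of 8.7 and on the absence, in either document, of a magnitude-based grade for laboratory or ECG AEs. The documents give no expected rate of such events, so the effect on any table cannot be estimated. It is worth correcting because it touches the primary objective and the values are already being recorded.

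**What to change.** 1. **Protocol 8.7:** state that AEs that are numeric laboratory, ECG-interval or vital-sign findings are graded by magnitude on a standard toxicity table that the sponsor adopts. Keep the functional wording for symptomatic AEs. Rhythm findings on telemetry have no measured value and fall outside the numeric rule.
2. **SAP 4.5.2:** derive the magnitude grade from the recorded values for all patients, including those enrolled under earlier amendments, so that pooled dose groups are on one scale. Use it in the severity tables and flag every DLT there. Record the change in SAP Section 5, which now says there are none.
3. **SAP 4.5.3:** add a count by dose group of peak ALT, AST and bilirubin in multiples of ULN, using each local laboratory's own limit.

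Cost: a protocol text change, which goes through the approval route in Protocol 10.2.3, and a little extra programming. No new data collection is needed. Some AEs now shown as Mild will move to a higher grade. No DLT, dosing or stopping rule changes.

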### **8.8** Action Taken for Adverse Event

Action taken in regards to study medication will be defined as:

- None;
- Infusion interrupted and restarted at a later time;
- Infusion stopped and was not restarted at a later time.

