**Planned Dose Cohorts and Enrollment Table 5-1:** 

#### 5.7 Criteria for Dose Escalation, Dose Modification or Discontinuation of **Study Drug**

#### 5.7.1 **Dose Escalation Procedures**

The initial dose of ALN-TTR02 is 10 µg/kg. Dose escalation to 50, 150, and 300 µg/kg is planned.

Within each of the cohorts, the first patient will receive their first dose and if the dose is well tolerated, per Section 5.7.3 (Dose-limiting Toxicity), Patients 2 and 3 will receive their first dose at that same dose level no sooner than 48 hours apart, with Patient 2 receiving a dose of study drug no sooner than 48 hours after the dosing of Patient 1. Similar to the first dose, the second dose will be administered to patients 4 weeks after the first dose in a sequential manner with at least 48 hours separating dosing of each patient. If after the first dose, ALT and AST are > 2.5 x ULN, that patient would not receive their second dose. Dose escalation to the next cohort will proceed after the collective safety and tolerability data through at least 96 hours post-first dose from the 3 patients in the previous cohort has been reviewed by the SRC. If the administered dose is found to be safe and well tolerated, dosing for the next cohort will begin no sooner than 96 hours after Patient 3 has safely received dose 1 from the previous cohort. Patients in the cohort would be dosed and reviewed for safety and tolerability following the same procedures as used for other cohorts (as stated above).

Up to 5 optional cohorts may be included to confirm the safety, tolerability, and/or PD effect of previously evaluated dose levels, which may include evaluation of the original dosing regimen (once every 4 weeks), an alternative dosing regimen (once every 3 weeks), and/or an alternative premedication regimen and infusion rate at a specific dose of ALN-TTR02. Dosing in these optional cohorts may occur at a previously tested dose that was found to be safe and where stopping rules were not met or at an intermediate dose level. Each optional cohort will be comprised of 3 patients.

For patients on all dose levels other than the starting dose level of  $10 \mu g/kg$ , prior to receiving the second dose the SRC will review the cumulative safety and tolerability data of at least 2 patients from the previous dose level(s) with at least 96 hours of follow-up after receiving a second dose of study drug.

The dosing of patients within each of the first 4 cohorts is depicted in

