### 8.4 Adverse Event Reporting

The Investigator is responsible for reporting all AEs that are observed or reported after the first dose of study drug regardless of their relationship to study drug through to Day 56.

Any medical condition that is present when a patient is screened and does not deteriorate should not be reported as an AE. However, if it does deteriorate at any time during the study, it should be reported as an AE.

All AEs must be fully recorded for 28 days from the start of infusion in the site's source records and in the patients' CRF, whether or not they are considered to be drug-related. Each AE should be described in detail: onset time and date, description of event, severity, relationship to investigational product, action taken, and outcome (including time and date of resolution, if applicable).

Adverse events should be followed for 28 days following the last dose of study drug or until recovery to the normal state has been achieved, whichever occurs first. In the event of a patient not returning to the clinical unit, the outcome of this event will be recorded as lost at follow up.

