### 9.2.3 Safety Analyses

A summary of study drug exposure, including the duration of the infusion and dose, and the proportion of patients with modifications in the duration of infusion will be produced.

Adverse events will be summarized by MedDRA system organ class and preferred term. Separate tabulations will be produced for all treatment emergent AEs, treatment-related AEs (those considered by the Investigator as at least possibly drug related), SAEs, and discontinuations due to AEs. By-patient listings will be provided for deaths, SAEs, DLTs, and events leading to discontinuation of treatment.

Descriptive statistics will be provided for clinical laboratory data, including cytokines, as well as vital signs data, presented as both actual values and changes from baseline relative to each on-study evaluation and to the last evaluation on study.

Descriptive statistics will be provided for ECG interval data and presented as both actual values and changes from baseline relative to each on-study evaluation and to last evaluation on study.

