1.2.5.2. Safety Parameters

Safety monitoring will include assessment of adverse events (AEs), 12-lead ECGs, cardiac monitoring (telemetry), arterial oxygen saturation (SaO₂) using pulse oximetry, vital signs (blood pressure, pulse rate, oral body temperature, and respiratory rate), clinical laboratory safety tests (hematology, serum chemistry, LFTs, thyroid function parameters, serology, coagulation parameters, urinalysis, cytokines, c-reactive protein [CRP], and complement factors), and physical examinations. Patients will be closely monitored for both acute and delayed IRRs. All IRRs will be recorded as AEs.

The safety of ALN-TTR02 will be evaluated by:

- The proportion of subjects experiencing AEs, serious adverse events (SAEs), DLTs, infusion-related AEs, and AEs leading to study drug discontinuation.
- Infusion tolerability, as assessed by serial ECGs, measurement of SaO₂ by pulse oximetry, and blood pressure.
- Change from baseline in clinical laboratory test results, including hematology, serum chemistries, LFTs, and coagulation parameters.
- Change from baseline in measures of thyroid function (thyroid stimulating hormone [TSH], T4, and triiodothyronine [T3]).
- Change from baseline in CRP, cytokines, and complement.
- Vital sign measurements.
- Physical examination findings.

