4.5.2. Adverse Events

Adverse events will be displayed in tables and data listings using MedDRA system organ class (SOC) and preferred term.

Analyses of AEs will be performed for those events that are considered treatment-emergent, where treatment-emergent is defined per protocol as any AE with onset during or after the administration of study medication through 28 days after dosing, or any event that was present pre-infusion but worsened in intensity or was subsequently considered drug-related by the Investigator.

When determining whether an AE is treatment-emergent, partial dates will be handled as follows. If the day of the month is missing, the onset day will be set to the first day of the month unless it is the same month and year as study treatment. In this case, in order to conservatively report the event as treatment-emergent, the onset date will be assumed to be the date of treatment. If the onset day and month are both missing, the day and month will be assumed to be January 1, unless the event occurred in the same year as the study treatment. In this case, the event onset will be imputed as the day of treatment, in order to report the event conservatively as treatment-emergent. A missing onset date will be imputed as the day of treatment. If the resulting imputed onset date is later than a non-missing date of resolution, then the imputed onset date will be set to the resolution date. The imputed data is used solely for the purpose of determining whether an AE is treatment-emergent; actual dates as recorded on the eCRF will be presented in subject listings.

Adverse events are summarized by subject incidence rates; therefore, in any tabulation, a subject contributes only once to the count for a given SOC or preferred term.

The numbers and percentages of subjects with any treatment-emergent adverse event (TEAE), with any TEAE assessed by the Investigator as related to treatment (definitely or possibly related), with any TEAE that is severe in intensity, with any serious TEAE, with any TEAE leading to discontinuation of study medication, or with any TEAE considered a DLT will be summarized by dose group and overall.

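### The protocol's action-taken list cannot record a second dose withheld because of an adverse event, and the SAP does not say how adverse events leading to discontinuation are identified

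*Protocol*

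**What the plan says.** Protocol 8.8 opens with "Action taken in regards to study medication will be defined as" and gives three values: none; "Infusion interrupted and restarted at a later time"; and "Infusion stopped and was not restarted at a later time". There is no entry for other. Section 8.4 makes action taken one of the details to be described for each adverse event.

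Treatment is two infusions, 4 weeks apart or 3 weeks in some optional cohorts. Several provisions can end a patient's treatment between them:

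- Sections 3.1 and 5.7.1: "If after the first dose, ALT and AST are > 2.5 x ULN, that patient would not receive their second dose".
- Sections 5.6 and 6.3.1.2 require eligibility to be confirmed again before dose 2.
- Section 5.7.4 halts all dosing after any DLT until the Safety Review Committee has reviewed the data.

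Section 7.4.1 foresees patients who receive only one dose and sets a PK schedule for them that runs to Day 208.

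On the analysis side, SAP 1.2.5.2 names "AEs leading to study drug discontinuation" among the safety measures. SAP 4.5.2 asks for the number and percentage of subjects "with any TEAE leading to discontinuation of study medication", by dose group and overall, and for a by-subject listing (Table 14.3.2.3). Protocol 9.2.3 asks for a tabulation of "discontinuations due to AEs" and a matching listing. Neither document says which recorded item marks an adverse event as having led to discontinuation.

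**The concern.** Apart from none, both values in 8.8 presuppose an infusion that is running. An adverse event that arises after dose 1 and costs the patient dose 2 interrupts no infusion, so the only literally true entry is none. The protocol prescribes an action that its own code list cannot record.

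Safety and tolerability are the primary objective, and discontinuation because of an adverse event is one of the few direct measures of tolerability in a two-dose study. Action taken is the only item described at the level of the individual adverse event that says what happened to study drug, so a programmer left without a rule would naturally turn to it. Built that way, the discontinuation row and listing can leave out patients who lost dose 2 for safety reasons.

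**Working it through.** The plan states no figure on this point, so the check is a comparison of texts followed by simple proportions.

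**Step 1. Match each written stopping route to the 8.8 values.**

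| Route | Where | Infusion running? | Value that fits |
|---|---|---|---|
| Severe acute infusion reaction | Protocol 5.11, Appendix 1 | Yes | Stopped, not restarted |
| ALT and AST above 2.5 × ULN after dose 1 | Protocol 3.1, 5.7.1 | No | Only none is literally true |
| Adverse event that fails the dose-2 eligibility re-check | Protocol 5.6, 6.3.1.2 | No | Only none is literally true |
| DLT after the infusion has ended, such as a severe delayed reaction | Protocol 5.7.4, Appendix 2 | No | Only none is literally true |

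**Step 2. Ask whether another planned output recovers the missing cases.**

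- Completion status. Protocol 4.5 requires both doses for completion, so a one-dose patient should appear as a non-completer in the SAP 4.1 disposition table. That status gives no cause.
- Withdrawal reason. Protocol 4.5.2 puts the primary reason on the CRF when a patient withdraws from the study. It is tied to leaving the study and is not linked to a particular adverse event. A patient whose dose 2 is withheld may stay in follow-up, as the one-dose PK schedule in 7.4.1 shows.
- DLT row and listing (SAP 4.5.2, Table 14.3.2.4). The enzyme criterion for a DLT in Protocol 5.7.3 is ALT and AST at or above 5 × ULN, while the withholding rule starts above 2.5 × ULN. A patient between the two levels loses dose 2 without meeting the enzyme criterion. The case is then a DLT only through another criterion, such as the committee's judgement.
- Dosing listing (SAP 4.5.1). It shows that the second infusion is absent, not which event was responsible.

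**Step 3. Look for the opposite error.** Protocol 5.11 leaves resumption after a moderate reaction to the investigator. An infusion abandoned at dose 1 on that ground would be coded as stopped and not restarted, and no provision bars dose 2 for that reason alone. Such a patient could receive dose 2 while carrying the only code that resembles discontinuation. Appendix 1 narrows this: a recurrence on re-challenge ends that patient's dosing, and a severe reaction is a DLT. What remains is mainly a mild or moderate reaction whose infusion was not resumed.

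**Step 4. Size of one uncounted patient.** Inputs are 3 patients per cohort (Protocol 4.4.1), pooling of cohorts with the same dose level and regimen (SAP 3.5), and 27 patients at full enrolment (SAP 3.1).

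- Single cohort: 1/3 = 33%, shown as 0/3.
- Two pooled cohorts: 1/6 = 17%, shown as 0/6.
- Overall: 1/27 = 3.7%, shown as 0/27.

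**The case against.** The strongest reply is that the under-count is conditional. A reader might infer that the discontinuation tables will omit every patient who loses dose 2 between infusions. The documents do not support that. They do not derive the tables from the 8.8 field, and the CRF itself is not among them. A different or additional field on the form could supply the flag. This stands, and it limits the conclusion to a possible under-count.

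A reader might also infer that stopping between doses is the main way treatment ends in this trial. The documents give no frequencies, and a severe reaction during an infusion, which 8.8 does capture, is a written stopping route too.

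It can further be said that little would stay hidden. DLTs have their own row and listing, a one-dose patient is by definition not a completer, and the SAP lists dosing and all adverse events by subject. With three patients in a cohort, a careful reader of the listings would notice a missing second infusion. This is fair mitigation, and it rules out saying that the drug would necessarily look better tolerated than it was. It does not repair the summary row or Table 14.3.2.3, because none of these sources ties the loss of dose 2 to the event that caused it.

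**Conclusion.** The recording gap is established from the text: the 8.8 list is closed and has no value for an action that the protocol prescribes. The missing definition in SAP 4.5.2 is equally plain. Together they mean that between-dose stops can be under-counted in a safety output that serves the primary objective.

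The size depends on an assumption, namely that the flag is taken from action taken. If it is, each affected patient moves a single-cohort result from 33% to 0%. These proportions illustrate one hypothetical patient and do not estimate an expected bias. The most exposed case is a liver-rule stop below the enzyme DLT threshold, because the DLT row may not catch it. The opposite error exists but is narrow. The point should be corrected; it does not call the design into question.

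**What to change.** In Protocol 8.8 and on the adverse event form, add a category such as *subsequent dose not given / study drug permanently discontinued because of this event*.

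In SAP 4.5.2, state that a TEAE led to discontinuation of study medication if it carries that category, or if the infusion was stopped and not restarted and no later dose was given. Cross-check the flag against the dosing record and the recorded reason for discontinuation. Report stopped infusions in patients who later received dose 2 separately, as incomplete infusions.

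The cost is one code list, one sentence in 8.8 and a short rule in the SAP. Sites have one more code to complete, and the reported discontinuation count may be less favourable. Only recording and analysis change; every clinical rule stays as it is.
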